4.0 STUDY DESIGN

4.1 Study Design Overview

This is an open-label, multicenter Phase 1b/2 study to determine the MTD and/or RP2D of ARRY-382 in combination with pembrolizumab in adult patients with selected advanced solid tumors (Part A/Phase 1b); and to estimate the efficacy of the combination in patients with advanced solid tumors that have progressed on prior PD-1/PD-L1 inhibitors, in patients with prOVCA and in patients with PDA (Phase 2).

Each phase of the study consists of a 28-day screening period; 21-day treatment cycles with the combination of ARRY-382 and pembrolizumab until disease progression as determined by the Investigator, unacceptable toxicity, withdrawal of consent, or death (or other discontinuation criteria are met [see also [Section 9.2](#)]); and a 30-day safety follow-up period. Patients in all cohorts/phases will be monitored for OS until 1 year after the date of the last patient's first visit.

Part A (Phase 1b) includes a dose-escalation component with 2 planned dose cohorts ([Table 6](#)). Oral doses of ARRY-382 will be administered QD in combination with pembrolizumab 2 mg/kg iv Q3W. Patients in Cohort 1 will be enrolled on a rolling basis up to 6 evaluable patients or until DLTs (see [Section 4.2](#)) are observed in more than 1 patient during Cycle 1. If fewer than 2 of 6 patients experience a DLT during Cycle 1, patients in Cohort 2 will receive ARRY-382 400 mg QD. If 2 or more patients in Cohort 1 experience DLTs during Cycle 1, the dosage of ARRY-382 in Cohort 2 will be 100 mg QD. If a Grade 3 immune-related AE (irAE) (first occurrence) is reported in a given cohort, enrollment in that cohort will continue at the same dose until the toxicity is evaluated. If a second Grade 3 irAE is reported or a first Grade 3 irAE is reported in addition to a previous DLT in a given cohort, enrollment of new patients in that cohort will be stopped until the Grade 3 irAE is evaluated. If the event is not a DLT (as determined by the Investigators in consultation with the Sponsor), then enrollment may be resumed, or the cohort may be expanded to include up to 9 patients. If the Grade 3 irAE is deemed a DLT, the MTD has been achieved and additional patients will be enrolled at the previous dose level or at an intermediate dose level.

Intermediate doses and doses higher than 400 mg QD may also be considered upon review of the safety and PK results from the planned dose cohorts.

Table 6: Planned Dose Cohorts (Part A)

	Planned dose regimen	

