8.2.2.2 Subsequent Cycles

8.2.2.2.1 Subsequent Cycles Day 1 (\pm 2 days)

- ECOG PS
- Physical exam, including body weight
- Vital signs, including blood pressure, pulse, and temperature
- Serum or urine pregnancy test (females of childbearing potential only)
- Triplicate 12-lead ECG over a period of approximately 5 to 10 minutes (Cycle 2 only)
 - Predose and 4 hours postdose

- Single 12-lead ECG (all cycles subsequent to Cycle 2)
- Blood sample for the following tests:
 - Clinical chemistry, thyroid panel, hematology, and coagulation
 - 
 - Pharmacokinetics
 - Cycle 2 only: Predose (i.e., within 120 minutes prior to administration of ARRY-382) and at 1, 2, 4, and 8 hours postdose
 - Cycles 3, 4, 5 and 6: Predose (i.e., within 120 minutes prior to administration of ARRY-382)
- Urine samples for the following tests:
 - Urinalysis
 - 
- Tumor assessments, i.e., imaging (e.g., CT, MRI, x-ray, FDG-PET) and caliper measurements, as applicable (Cycle 3 Day 1 [± 7 days] and approximately every 6 weeks thereafter [e.g. Cycle 5 Day 1 [± 7 days], Cycle 7 Day 1 (± 7 days), etc.]
- Administration/dispensing of ARRY-382
- Administration of pembrolizumab
- Review of concomitant medications
- Review of AEs

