- c. All prior cancer treatments are to be recorded; other prior treatments (i.e., other than cancer treatments) taken within 4 weeks of screening should also be recorded.
- d. These assessments do not need to be repeated if they were performed within 96 hours of Cycle 1 Day 1. For the triplicate 12-lead ECG, the predose assessment need not be repeated if it was performed within 96 hours of Cycle 1 Day 1, but the assessment at 4 hours postdose must be performed regardless of when the predose assessment was performed.
- e. Physical examination includes height at screening only.
- f. Vital signs include blood pressure, pulse, and temperature.
- g. For females of childbearing potential only (see [Section 7.1.2](#)), serum pregnancy tests are to be performed at screening; serum or urine pregnancy tests will be allowed at subsequent time points.
- h. All patients are to have a fresh biopsy plus a blood sample obtained at screening, or submit archived tumor samples from the most recent sample available plus a blood sample. The requirement of tumor tissue may be waived only with Sponsor approval (see [Section 7.1.5](#)).
- i. Three 12-lead ECGs are to be performed over a period of approximately 5 to 10 minutes. Triplicate 12-lead ECGs will be performed at predose and 4 hours (± 10 minutes) for all postbaseline assessments.
- j. For subsequent cycles, triplicate 12-lead ECGs are to be performed on Day 1 of Cycle 2 only.
- k. Single 12-lead ECGs will be performed on Cycle 3 Day 1 and Day 1 of subsequent cycles.
- l. Clinical chemistry and hematology tests are to be performed on Day 15 of Cycles 2, 3, and 4 only. For Cycles ≥ 5 , the Day 15 visit can be replaced with a telephone call to assess AEs and concomitant medications.

C
C
I

- o. Tumor assessments include imaging (e.g., CT, MRI, x-ray, FDG-PET) and caliper measurements, as applicable.
- p. Tumor assessments are to be performed on Cycle 3 Day 1 (± 7 days) and approximately every 6 weeks thereafter (e.g., Cycle 5 Day 1 [± 7 days], Cycle 7 Day 1 [± 7 days], etc.).
- q. Tumor assessments are to be performed only if clinically indicated. Patients who discontinue the study for a reason other than disease progression should be encouraged to continue with tumor assessments every 8 weeks ± 1 week until disease progression as determined by the Investigator, withdrawal of consent, initiation of subsequent anticancer therapy, the patient is lost to follow-up, or death, whichever occurs first.

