9.2 Treatment Discontinuation for Individual Patients

Patients may withdraw their consent to participate in the study at any time for any reason without prejudice to their future medical care by the physician or at the institution. If a patient withdraws consent, the date and stated reason for consent withdrawal should be documented. Patient data collected up to the date of consent withdrawal will be included in the analyses. Any blood or tissue samples collected up to the date of consent withdrawal will be analyzed.

Wherever possible, the tests and evaluations listed for the Treatment Discontinuation Visit should be carried out and efforts should be made to continue follow-up. The Sponsor should be notified of all study withdrawals through the designated eCRFs in a timely manner.

Patients meeting any of the following criteria should discontinue study drug treatment:

- Withdrawal of consent (no further participation and thus no further protected health information may be collected)
- Patient decision to discontinue study treatment (but agree to return for treatment discontinuation assessments ([Section 8.3](#)), safety follow-up ([Section 8.4](#)) and/or additional follow-up, if applicable ([Section 8.5](#) and [Section 8.6](#)))
- Unacceptable AEs or failure to tolerate study drug
Note: For patients with melanoma, single-agent treatment with ARRY-382 is not recommended; if pembrolizumab is permanently discontinued for these patients, ARRY-382 must also be discontinued.
- Delay of > 21 days to start a subsequent treatment cycle unless judged by the Investigator to be in the best interest of the patient to continue treatment
- Changes in the patient's condition or development of an intercurrent illness which renders the patient unacceptable for further treatment in the judgment of the Investigator
- Disease progression, as determined by the Investigator

- Patient becomes pregnant or begins breastfeeding
- Significant protocol deviation that, in the opinion of the Investigator and/or Sponsor, renders the patient unsuitable for further study drug administration
- Lost to follow-up
- Discretion of Investigator
- Termination of the study by the Sponsor (described in [Section 9.1](#))

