1.4 Methods of Measurement

The same method of assessment and the same technique should be used to characterize each identified and reported lesion at baseline and during follow-up. Assessments should be identified on a calendar schedule and should not be affected by delays in therapy, which may be treatment-arm dependent. While on study, all lesions recorded at baseline should have their actual measurements recorded at each subsequent evaluation, even when very small (e.g., 2 mm). If it is the opinion of the radiologist that the lesion has likely disappeared, the measurement should be recorded as 0 mm. If the lesion is believed to be present and is faintly seen but too small to measure, a default value of 5 mm should be assigned. For lesions which fragment/split add together the longest diameters of the fragmented portions; for lesions which coalesce, measure the maximal longest diameter for the “merged lesion”.

Clinical lesions: Clinical lesions will only be considered measurable when they are superficial and ≥ 10 mm diameter as assessed using calipers (e.g., skin nodules). For the case of skin lesions, documentation by color photography including a ruler to estimate the size of the lesion is suggested. If feasible, imaging is preferred.

Chest X-ray: Chest CT is preferred over chest X-ray, particularly when progression is an important endpoint, since CT is more sensitive than X-ray, particularly in identifying new lesions. However, lesions > 20 mm on chest X-ray may be considered measurable if they are clearly defined and surrounded by aerated lung.

CT, MRI: CT is the best currently available and reproducible method to measure lesions selected for response assessment. This guideline has defined measurability of lesions on CT scan based on the assumption that CT slice thickness is 5 mm or less. When CT scans have slice thickness greater than 5 mm, the minimum size for a measurable lesion should be twice the slice thickness. MRI is also acceptable in certain situations (e.g., for body scans). While PET scans are not considered adequate to measure lesions, positron emission tomography-computerized tomography [PET-CT] scans may be used providing that the measures are obtained from the CT scan and the CT scan is of identical diagnostic quality to a diagnostic CT (with intravenous [iv] and oral contrast).

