### 7.5.3 Progression-free Survival

PFS is defined as the time from the date of first dose of study drug to the earliest date of disease progression, as determined by Investigator review of radiographic disease assessments per RECIST v1.1, or death due to any cause.

If a patient has not had a PFS event at the time of the analysis cutoff or at the start of any new anticancer therapy, PFS will be censored at the date of last adequate tumor assessment. If a PFS event is observed after more than one missing or inadequate tumor assessment, PFS will be

censored at the last adequate tumor assessment. If a PFS event is observed after a single missing or non-adequate tumor assessment, the actual date of event will be used. Patients who do not have baseline or post-baseline tumor assessments will be censored at the study start date.

The last adequate tumor assessment is defined as a tumor assessment result that is not “NE”, “ND”, “NA” or missing.

The survival distribution function for PFS will be estimated using the Kaplan-Meier (KM) method as described for DOR in Section 7.5.2. The PFS rate at 2, 4 and 6 months will be estimated with corresponding two-sided 95% CIs.

Frequency counts and percentages of patients with each event type (PD or death) and censoring reasons will be summarized as described in Section 7.5.2.

In addition, time to progression/censoring, event and censoring reasons will be listed.

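### The first tumour scan is anchored to Cycle 3 Day 1, which can slip when both drugs are held; this contradicts the calendar rule in Appendix 5 and distorts PFS timing in delayed patients, in either direction

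*Protocol*

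**What the plan says.** Protocol Section 7.2 refers sites to Tables 10 and 11 for the timing of tumour assessments. Footnote p to Table 11 (Phase 2) reads "Tumor assessments are to be performed on Cycle 3 Day 1 (± 7 days) and approximately every 6 weeks thereafter", and footnote p to Table 10 (Part A) has the same anchor. Section 8.2.2.2.1 lists the scan among the Day 1 procedures of later cycles: "caliper measurements, as applicable (Cycle 3 Day 1 [± 7 days] and approximately every 6 weeks thereafter". Section 8.2.1.2.1 does the same for Part A. The later cycle labels are examples only: "approximately every 6 weeks thereafter (e.g., Cycle 5 Day 1".

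Section 4.1 plans "21-day treatment cycles with the combination of ARRY-382 and pembrolizumab until disease progression". Cycles can move, however. Section 6.3.1 stops both drugs when a toxicity cannot be attributed to one of them. Section 6.3 lets the next cycle restart with either drug. Section 9.2 makes this a reason to discontinue: "Delay of > 21 days to start a subsequent treatment cycle unless judged by the Investigator". A delay of up to 21 days is therefore within the plan.

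Appendix 5 section 1.4 says: "Assessments should be identified on a calendar schedule and should not be affected by delays in therapy, which may be treatment-arm dependent".

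On the analysis side, SAP 7.5.3 states: "The PFS rate at 2, 4 and 6 months will be estimated with corresponding two-sided 95% CIs". It censors a PFS event that follows more than one missing or inadequate assessment, and SAP 7.5.2 lists the matching censoring reasons. SAP 7.5.1 counts PD as best response only up to 9 weeks from the start of treatment. A later first PD with no scan in between is Not Evaluable.

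**The concern.** A cycle day is not a calendar day. If Cycle 3 Day 1 slips, a site reading the schedule table postpones the first scan, and the later scans, counted at 6-week intervals from it, slip too. A site reading Appendix 5 scans the same patient on the original date. Neither the tables nor Section 8.2 repeats the calendar rule.

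Progression is dated by the scan that shows it. The timing of PFS, irPFS and best-response data would then depend on whether toxicity interrupted dosing and on which passage the site followed. The missed-assessment rule also cannot be applied consistently while two clocks exist.

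**Working it through.** **Inputs from the documents.** First scan at Cycle 3 Day 1 ± 7 days (Protocol Table 11, footnote p); 21-day cycles (Protocol 4.1); cycle-start delay of up to 21 days (Protocol 9.2); 1 month = 30.4375 days (SAP 7.1.7); PFS landmarks at 2, 4 and 6 months (SAP 7.5.3); 9-week PD limit (SAP 7.5.1).

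**Assumptions.** Progression times are exponential with medians of 1.9 and 3.0 months. Protocol 2.1.4 cites these values for pembrolizumab in PD-L1-positive ovarian cancer and, approximately, for single-agent chemotherapy in platinum-resistant disease. Scans are on their nominal day, progression is dated at the next scan, and there are no deaths. The share of patients delayed is not in the documents; I take 10% to 50%.

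**1. The plan's own schedule, no delay.** Elapsed days at Cycle c Day 1 = (c − 1) × 21. Cycles 3, 5 and 7 give 42, 84 and 126 days, that is weeks 6, 12 and 18, or study Days 43, 85 and 127. The cycle labels and the 6-week interval agree.

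**2. With a delay of d days before Cycle 3.** First scan = Day 43 + d.
- d = 7: Day 50, the edge of the calendar window (Days 36-50).
- d = 14: Day 57.
- d = 21: Day 64 (window 57-71).
- 21 days before both Cycle 2 and Cycle 3: 43 + 42 = Day 85 (window 78-92).

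Any slip over 7 days puts the nominal scan outside the calendar window.

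**3. PFS landmarks after one 21-day slip.** The landmarks are 2 × 30.4375 = 60.9, 4 × 30.4375 = 121.75 and 6 × 30.4375 = 182.6 days. The observed rate at a landmark is S(t) at the last scan before it, with S(t) = 2^(−t/M) and M = 1.9 × 30.4375 = 57.8 or 3.0 × 30.4375 = 91.3 days.

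| Landmark | Last scan, calendar (elapsed days) | Last scan, slipped | Rate, median 1.9 | Rate, median 3.0 |
|---|---|---|---|---|
| 2 months | 42 | none | 60% → 100% | 73% → 100% |
| 4 months | 84 | 105 | 37% → 28% | 53% → 45% |
| 6 months | 168 | 147 | 13% → 17% | 28% → 33% |

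The 2-month jump needs a slip of at least 18 days (43 + 18 = Day 61). With a 14-slip-day scan (56 elapsed days) the 2-month rate falls instead: 2^(−56/57.8) = 51% against 60%, and 2^(−56/91.3) = 65% against 73%. Similarly, after a 21-day slip a scan taken on Days 57-60 of its window still precedes the landmark.

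For the whole cohort, multiply by the share delayed. At 2 months: 0.10 × 27 to 0.50 × 40, or about 3 to 20 percentage points.

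**4. Mean and median.** Mean observed PFS on the calendar is 42/(1 − S(42)), which is 106.2 days for a 1.9-month median. After a 21-day slip it is 63 + S(63) × 106.2 = 63 + 0.470 × 106.2 = 112.9 days, a rise of 6.7 days. For a 3.0-month median the rise is 4.5 days. With 10% to 50% delayed, the cohort mean moves by 0.10 × 4.5 to 0.50 × 6.7, or about 0.5 to 3.4 days. The observed median falls, from 84 to 63 days (1.9 months) and from 126 to 105 days (3.0 months). With a 14-day slip it rises from 84 to 98 in the first case and falls from 126 to 98 in the second.

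**5. Best response.** 9 × 7 = 63 elapsed days = Day 64. After one 21-day slip, a first scan showing PD on Days 65-71 of the 57-71 window is Not Evaluable. After two, the whole window is. If weeks were counted by the inclusive day count of SAP 7.1.7, Day 64 would also be past the limit.

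**6. Primary analysis.** PD and Not Evaluable are both non-responses, so that reclassification leaves ORR unchanged. Recomputing the Simon designs gives type I error 0.0990, power 0.804, early stopping 0.599 and expected size 14.6 for prOVCA, and 0.0992, 0.801, 0.542 and 21.4 for PDA. These match the stated figures, and none depends on scan dates.

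**The case against.** The strongest reply is that the protocol already holds the rule. Section 7.2.1 applies Appendix 5, Appendix 5 puts scans on a calendar, and no footnote tells a site to postpone a scan during a hold. The Version 3 change log, as context only, gives the same intent. This shows what the sponsor wants, but not that sites will do it: Section 7.2 sends them to the tables, whose text gives a cycle day and no calendar rule.

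Other parts of the reply stand and limit the point:
- A reader might infer that the scan clock is tied to Cycle 5 and Cycle 7 Day 1. It is not; those are examples of a 6-week interval, and only the first scan has a cycle anchor.
- A reader might infer that any dosing hold delays the scan. It does not. The other drug may continue (6.3.1), either drug may restart a cycle (6.3), and Day 1 trough samples are still drawn while ARRY-382 is held (Table 11, footnote s). A slip needs both drugs held across a cycle boundary.
- A reader might infer that toxicity uniformly lengthens PFS, or that sites following Appendix 5 will report shorter PFS. Neither follows. A patient who progresses on Day 50 is dated Day 85 on the calendar but Day 64 after a 21-day slip.
- Off-schedule imaging is foreseen (Protocol 7.2), and unscheduled data are generally analysed (SAP 7.1.8), so some progressions would be caught between scans.
- PFS is secondary and descriptive, with no control arm. The SAP was written to protocol Version 5, which is not available here, so the schedule wording in that version should be checked.

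**Conclusion.** The point holds as an internal contradiction with a limited analytic effect. The schedule tables and Section 8.2 set the first scan by a day that can slip from Day 43 to Day 64 after one 21-day delay of both drugs; Appendix 5 says delays in therapy must not move it.

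In delayed patients the result is distorted timing, not consistently longer PFS. Under the exponential assumptions, a 21-day slip leaves no nominal scan before the 2-month landmark, lowers the 4-month rate by 8 to 9 points and lowers the observed median, while the mean rises by 4.5 to 6.7 days. Some early progressors would be tabulated as Not Evaluable. The cohort effect scales with a share of delayed patients that the documents do not give. ORR and the Simon error rates are unaffected. The passages should be reconciled because the conflict makes scan timing depend on toxicity and site reading, and the correction is cheap.

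**What to change.** In footnote p of Tables 10 and 11 and in Sections 8.2.1.2.1 and 8.2.2.2.1, anchor scans to Cycle 1 Day 1: Day 43 ± 7 days, then every 6 weeks ± 7 days counted from Cycle 1 Day 1, regardless of dose interruptions or cycle delays. Remove the Cycle 5 and Cycle 7 examples, or relabel them as weeks 12 and 18. In SAP 7.5.2 and 7.5.3, state that missed assessments are counted on this same calendar.

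This is a change of wording that matches Appendix 5 and adds no planned scans. The small cost is that a scan may fall on a day without a dosing visit.

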9.0 STUDY DISCONTINUATION

9.1 Sponsor Discontinuation Criteria

This study may be discontinued at any time due to safety concerns, failure to meet expected enrollment goals, administrative reasons, or at the discretion of the Sponsor. Should the study be terminated prematurely, the Sponsor will provide written notification to all Investigators and regulatory authorities and will specify the reason(s) for early termination. The Investigator must inform the Institutional Review Board (IRB) promptly and provide the reason(s) for the termination.

9.2 Treatment Discontinuation for Individual Patients

Patients may withdraw their consent to participate in the study at any time for any reason without prejudice to their future medical care by the physician or at the institution. If a patient withdraws consent, the date and stated reason for consent withdrawal should be documented. Patient data collected up to the date of consent withdrawal will be included in the analyses. Any blood or tissue samples collected up to the date of consent withdrawal will be analyzed.

Wherever possible, the tests and evaluations listed for the Treatment Discontinuation Visit should be carried out and efforts should be made to continue follow-up. The Sponsor should be notified of all study withdrawals through the designated eCRFs in a timely manner.

Patients meeting any of the following criteria should discontinue study drug treatment:

- Withdrawal of consent (no further participation and thus no further protected health information may be collected)
- Patient decision to discontinue study treatment (but agree to return for treatment discontinuation assessments ([Section 8.3](#)), safety follow-up ([Section 8.4](#)) and/or additional follow-up, if applicable ([Section 8.5](#) and [Section 8.6](#)))
- Unacceptable AEs or failure to tolerate study drug
Note: For patients with melanoma, single-agent treatment with ARRY-382 is not recommended; if pembrolizumab is permanently discontinued for these patients, ARRY-382 must also be discontinued.
- Delay of > 21 days to start a subsequent treatment cycle unless judged by the Investigator to be in the best interest of the patient to continue treatment
- Changes in the patient's condition or development of an intercurrent illness which renders the patient unacceptable for further treatment in the judgment of the Investigator
- Disease progression, as determined by the Investigator

- Patient becomes pregnant or begins breastfeeding
- Significant protocol deviation that, in the opinion of the Investigator and/or Sponsor, renders the patient unsuitable for further study drug administration
- Lost to follow-up
- Discretion of Investigator
- Termination of the study by the Sponsor (described in [Section 9.1](#))

